5.3. Medical History

Medical history will be summarized based on the SAF population.

Summary tables will be sorted by decreasing frequency of SOC followed by PT.

5.4. Prior/Concomitant Medications and Procedures

The prior and concomitant medications will be presented for FAS. Number and proportion of subjects taking concomitant medications, prohibited medications/procedures and rescue medications/procedures will be summarized based on FAS, sorted by decreasing frequency of ATC Level 2 and ATC level 4 according to the World Health Organization Drug Dictionary.

5.5. Measurement of Compliance

Compliance will be assessed and summarized by actual treatment within SAF. The compliance with protocol-defined investigational product will be calculated as follows:

Treatment Compliance = (Number of study drug injections during exposure period)/(Number of planned study drug injections during exposure period) x 100%

The percentage of subjects who have <70%, and >=70% compliance will be summarized for each group.

5.6. Extent of Study Treatment Exposure

The extent of treatment exposure will be assessed and summarized by actual treatment within SAF. Exposure to study treatment will be examined for each subject and the following variables will be summarized:

- The total number of study doses administered
- Duration of treatment exposure (in weeks) calculated as:
- (Date of last study drug injection – date of first study drug injection + 14 days)/7

The number of subjects exposed to study drug will be presented by specific time point periods for each group. The time periods of interest are weeks 2, 4, 6, 8, 12.

5.7. Analysis of Efficacy Data

The efficacy analyses will be performed based on the FAS according to assigned treatment group.

5.7.1. Analysis of Primary Efficacy Variable

The primary endpoint of change from baseline in constant work rate exercise endurance time at week 12 will be descriptively summarized.

Please note that the primary endpoint of change from baseline in constant work rate exercise endurance time at week 12 was originally planned to be analyzed using ANCOVA model for the

FAS with treatment group, randomization stratification factor, and relevant baseline measurement as covariates included in the model.

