11. STATISTICAL PLAN

This section provides the basis for the statistical analysis plan (SAP) for the study. The SAP will be revised prior to the end of the study to accommodate amendments to the clinical study protocol and to make changes to adapt to unexpected issues in study execution and data that may affect the planned analyses. The final SAP will be issued before the database lock.

Endpoints are listed in Section 4. Analysis variables are listed in Section 5.

Data collected through the implementation of CRFs regarding the impact of the COVID-19 pandemic on patients will be summarized (eg, discontinuation due to COVID-19). Any additional analyses and methods required to investigate the impact of COVID-19 on the efficacy (eg, missing data due to COVID-19) and safety evaluation will be specified in the SAP.

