11.4.3. Efficacy Analyses

11.4.3.1. Primary Efficacy Analysis

The primary endpoint of change from baseline in constant work rate exercise endurance time at week 12 will be analyzed using an analysis of covariance (ANCOVA) model for the FAS population. The ANCOVA model will include terms for treatment group, randomization stratification factors and the baseline value for the constant work rate exercise endurance time.

The intercurrent events handling strategy for systemic corticosteroid use for an asthma exacerbation or an increase in systemic corticosteroids during last 4-week of the treatment period and for treatment discontinuation is specified in [Table 3](#) (Primary Estimands). The imputation method for missing data based on the reasons for study discontinuation is defined below:

- Missing data due to:
 - AE or lack of efficacy will be imputed by baseline observation carried forward (BOCF).
 - Other reasons will be imputed using multiple imputation (MI) rules under a missing at random assumption. A detailed imputation model will be specified in the SAP.

The primary estimands of interest for the primary endpoint, definitions of intercurrent events and corresponding strategies, and missing data handling approaches are provided in [Table 3](#):

Table 3: Primary Estimands

Endpoint category	Estimands			
	Endpoints	Population	Intercurrent event(s) handling strategy and missing data handling	Population-level summary/Analysis method

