1. OVERVIEW

The purpose of the statistical analysis plan (SAP) is to ensure the credibility of the study results by pre-specifying the statistical approaches for the analysis of study data prior to database lock. The SAP is intended to be a comprehensive and detailed description of the strategy and statistical methods to be used in the data analysis of R668-AS-1903

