1.3.1. Hypothesis

The pre-defined hypothesis was that patients with moderate-to-severe asthma treated with dupilumab would show improvement in exercise capacity and increase in physical activity of daily living. However, due to under enrollment, study is not sufficiently powered for the primary endpoint. Therefore, there will be no formal hypothesis testing for any of the specified endpoints in the study.

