2.2. Statistical Hypothesis

The following null and alternative hypotheses are specified for reference. There is no formal hypothesis testing. All p-values will be nominal and for exploratory and hypothesis-generating purposes only.

- Null hypothesis: The mean change from baseline in the constant work-rate exercise endurance time at week 12 is the same between dupilumab and placebo.
- Alternative hypothesis: The mean change from baseline in the constant work rate exercise endurance time at week 12 differs between dupilumab and placebo.

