2.3. Sample Size and Power Considerations

The originally planned sample size of approximately 70 patients per treatment group (N=140 total) was to provide >85% power to detect a 105-second mean change in exercise endurance time, with a standard deviation of 190 seconds, 2-sided $\alpha = 5\%$, and 10% drop out rate. However, due to enrollment challenges, the study will be terminated early at a smaller-than-planned sample size, and all the analyses will be exploratory (with no alpha control).

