5. STATISTICAL METHODS

For continuous variables, descriptive statistics will include the following: the number of patients reflected in the calculation (n), mean, standard deviation, first quartile (Q1), median, third quartile (Q3), minimum, and maximum.

For categorical or ordinal data, frequencies and percentages will be displayed for each category.

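### Under-enrolment justifies dropping the formal test of the primary endpoint, but the SAP also drops the between-arm estimate that the protocol ANCOVA would have given

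*SAP*

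**What the plan says.** Protocol 11.1 states hypotheses about the difference between arms in mean change in endurance time at week 12. Protocol 11.4.3.1 gives the model: "The ANCOVA model will include terms for treatment group, randomization stratification factors and the baseline value for the constant work rate exercise endurance time". Table 3 of the protocol repeats it and adds rules for intercurrent events and missing data. Neither document names a confidence interval; the treatment contrast and its 95% CI are implied by the model and the two-sided 5% level.

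SAP 5.7.1 substitutes a descriptive summary: "The primary endpoint of change from baseline in constant work rate exercise endurance time at week 12 will be descriptively summarized". It notes beside this that an ANCOVA with treatment, stratification factor and baseline was the plan originally. SAP 5 defines the summary for a continuous variable: "descriptive statistics will include the following: the number of patients reflected in the calculation (n), mean, standard deviation", followed by quartiles and range. SAP 5.7 presents efficacy by assigned group. SAP 1.3.1 gives the reason: "due to under enrollment, study is not sufficiently powered for the primary endpoint". SAP 2.2 keeps the between-arm hypotheses for reference and adds: "All p-values will be nominal and for exploratory and hypothesis-generating purposes only". SAP 4.4 also calls p-values nominal and allows additional methods. SAP 6.1 plans no imputation.

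Two protocol passages bear on whether this change is allowed. Section 11 lets the SAP be revised "to make changes to adapt to unexpected issues in study execution and data that may affect the planned analyses". Section 11.6 restricts which parameters are summarized after premature termination.

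**The concern.** The stated reason covers less than the step taken. Low power means that a test is likely to miss a real effect. It does not mean that the difference cannot be estimated, and a wide interval is the honest way to show how little about 40 patients can say. The SAP still reports the primary endpoint and still states between-arm hypotheses, yet it plans nothing that compares the arms.

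The SAP is also incomplete in its own terms. Its stated purpose is "to ensure the credibility of the study results by pre-specifying the statistical approaches for the analysis of study data prior to database lock". It refers to nominal p-values, but no planned test or model produces one. It records the original model without planning to use it. If a difference appears in the report, the SAP will not have said which difference it should be.

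Missing data raise a narrower point. Under protocol Table 3, a patient given systemic corticosteroids for an exacerbation in the last 4 weeks was assigned the baseline value. Dropout for AE or lack of efficacy was handled by BOCF, and other missing values by multiple imputation. Under SAP 6.1 all of these patients simply leave the summary. The tabled n will show this, but the SAP does not say that it departs from Table 3.

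**Working it through.** **Inputs.** Effect 105 s, SD 190 s, two-sided 5%, 10% dropout, about 70 per arm (protocol 11.2, SAP 2.3). About 40 patients at termination and 1:1 allocation (SAP 2.1). I assume 20 per arm, or 18 after 10% dropout, and that the SD of 190 s still applies.

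**1. The plan's own figure.** SE = SD × √(2/n). With n = 70 × 0.9 = 63, SE = 33.9 s and 105/33.9 = 3.10. The two-sample t-test has 86.8% power, which agrees with the stated figure of more than 85%.

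**2. Power at the reduced size.** With n = 20, SE = 60.1 s and 105/60.1 = 1.75, giving 39.9%. With n = 18, SE = 63.3 s and 105/63.3 = 1.66, giving 36.4%.

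**3. What can still be estimated.** The crude 95% half-width is t × SE.
- 63 per arm: 1.979 × 33.9 = 67 s
- 20 per arm: 2.024 × 60.1 = 122 s
- 18 per arm: 2.032 × 63.3 = 129 s

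An observed 105 s with 20 per arm would have an interval of about −17 to 227 s. If the SD were 150 to 230 s, the half-width at 20 per arm would be 96 to 147 s.

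**4. Crude against adjusted.** The effect of adjustment depends on r, the correlation of baseline endurance time with its change, which the documents do not give. I assume baseline times spread evenly over the 180 to 480 s run-in window, so the SD is 300/√12 = 87 s. With a change SD of 190 s, baseline to week-12 correlations from 0 to 0.70 give r from −0.46 to +0.43. I therefore take |r| from 0 to 0.46.

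The simulation used 40 patients, no true effect, change SD 190 s and four patients on maintenance OCS. Further assumptions are stratified blocks of 4 (no block size is documented), 35% in the smaller FEV₁ and age strata, and strata that do not predict outcome. The adjusted model has baseline and three stratification factors.

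| r (absolute) | Crude half-width | Adjusted half-width | Median absolute difference, crude vs adjusted |
|---|---|---|---|
| 0 | 121 s | 125 s | 8 s |
| 0.15 | 121 s | 124 s | 9 s |
| 0.30 | 121 s | 119 s | 12 s |
| 0.46 | 121 s | 111 s | 18 s |

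As a hand check, chance baseline imbalance alone moves the estimate by a median of 0.6745 × r × 190 × √(2/20). That is 12 s at 0.30 and 19 s at 0.46. At low r the formula falls short, because the movement comes mostly from noise in the fitted slopes. Using two or three stratification factors changes the estimate by a median of only about 2 s.

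**5. Can the model be fitted?** The 10% cap allows about 4 OCS patients in 40. In the worst case all four fall in one arm of 20. The correlation of OCS use with treatment is then (4×20 − 0×16)/√(20×20×4×36) = 80/240 = 1/3, and the treatment SE rises by a factor of 1/√(1 − 1/9) = 1.06. The main-effects model stays estimable, so no rule for dropping the OCS term is needed.

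**The case against.** The strongest reply is that the change is open, reasoned and permitted. SAP 1.3.1, 2.3 and 5.7.1 disclose it, protocol 11 foresees such adaptation, and protocol 11.6 foresees reduced reporting. This stands as far as it goes. A reader who inferred a concealed deviation would be wrong. But 11.6 limits which parameters are summarized, not how a primary endpoint that is still reported is analysed, and disclosure does not supply an estimate.

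A second reply is that little is lost, because a crude difference and interval follow from n, mean and SD. That is also true, and adjustment may even widen the interval slightly. What cannot be rebuilt is the baseline- and strata-adjusted estimate that the protocol described.

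A third reply is that the original model is on record in both documents, so a later estimate could be checked against it. This too stands. It would go too far to say that any reported estimate must have been chosen after seeing the data: SAP 4.4 only permits additional methods, and SAP 5.7.1 names the original covariates.

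On missing data, SAP 5.1 tabulates reasons for discontinuation and SAP 5.4 tabulates rescue medication. Neither shows why a patient still in the study has no week-12 CWRET.

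**Conclusion.** The point holds as an inexpensive improvement. Power of about 36% to 40% supports dropping the formal test. It does not support leaving the primary endpoint without a between-arm estimate and interval, when the SAP still states between-arm hypotheses and the model is already written.

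The gain is pre-specification and visible uncertainty, not precision. The half-width is about 122 to 129 s crude, wider than the 105 s planning effect, and 111 to 125 s adjusted with 40 patients. The median crude-to-adjusted difference of 8 to 18 s is 7% to 15% of the 121 s half-width (8/121 and 18/121).

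Two stronger readings are not supported. First, the protocol did not explicitly promise a 95% CI; the interval is only implied by the ANCOVA. Second, the choice of model should not be expected to move the result by a large share of the 105 s effect. Such figures arise only in the upper tail of simulations that compare the most extreme of several models, a contest that the SAP does not plan.

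The figures rest on an SD of 190 s, 18 to 20 per arm, the assumed range of r and the simulation assumptions listed above.

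**What to change.** Before database lock:

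- Reconcile the stratification factors. The protocol synopsis and 8.7 list FEV₁, maintenance OCS use and age; protocol 6.1 and SAP 2.1 list only FEV₁ and age. Use the factors that the IWRS actually applied.
- State in SAP 5.7.1 that the protocol ANCOVA will be fitted to observed week-12 data as an exploratory analysis, with treatment, baseline endurance time and those factors as main effects. Report the adjusted mean difference with a 95% CI, without formal testing or alpha control, beside the descriptive summary.
- Tie the nominal p-values in SAP 2.2 and 4.4 to this model, or delete that wording.
- State that the observed-case analysis under SAP 6.1 departs from protocol Table 3, and tabulate by arm the reasons for a missing week-12 CWRET, including late systemic corticosteroid use.

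The cost is SAP wording, one standard model and one small table, with no new data or patients. The downside is a few degrees of freedom and an interval that will be wide.

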5.7.2. Analysis of Key Secondary Efficacy Variable

Pre-exercise FEV1 will be assessed within 15 minutes prior to the start of the exercise testing and post-exercise FEV1 will be performed at minutes 5±1, 10±1, and 20±1 post-exercise. Pre-exercise FEV1 and Post-exercise FEV1 will be analyzed descriptively.

Continuous secondary efficacy endpoints that are to be measured by accelerometry will be summarized. 7-day average values of measurements from accelerometry are calculated for baseline and week 12 if days with a wear time of at least 22 hours (accounting for non-wear periods as permissible in protocol) and at least 5 valid days per week are available.

5.7.3. Analysis of Exploratory Variables

5.7.3.1. Measurements associated with CPET

Continuous secondary efficacy endpoints that are to be measured associated with CPET will be analyzed in the same fashion as the primary endpoint.

5.7.3.2. Patient Diary

7-day average values of measurements from patient diary are calculated for baseline and week 12 and will be summarized descriptively if at least 5 valid days per week are available.

Additionally, the same analysis is repeated for patients with at least 4 valid days per week.

- Change from baseline to week 12 in number of nocturnal awakenings per night due to asthma from patient diary

5.7.3.3. Spirometry not associated with CPET

Pre-exercise FEV1 and FVC at baseline will be used as baseline value. Change from baseline in FEV1 and FVC at week 4 will be summarized.

5.7.3.4. Patient-Reported Outcomes

PRO data (ACQ-5, AQLQ(S), PGIC, PGII) will be summarized descriptively, as described in Section 4

5.8. Analysis of Safety Data

The analysis of safety and tolerability will be performed on the SAF. The summary of safety results will be presented by treatment group and in overall total.

5.8.1. Adverse Events

The verbatim text, the preferred term (PT), and the primary system organ class (SOC) will be displayed in subject listings. Summaries that include number and proportions of patients reporting AEs will include the PTs and the SOCs.

Period of observation: The observation period will be divided into three periods: pre-treatment, on-treatment and post-treatment.

- The pre-treatment period is defined as the time between signing the ICF to before the first dose of study drug.
- The on-treatment period is defined as the time from the date of the first dose of study drug to the week 12 visit date (study day 85 starting from the first dose of study drug if week 12 visit date is unavailable) or early termination date, whichever comes first.
- The post-treatment period is defined as days from the date after week 12 visit date (study day 85 starting from first dose of study drug if week 12 visit date is unavailable) to end of study.

Treatment-emergent AEs are defined as AEs that developed or worsened during the on-treatment period and post-treatment period.

Summaries of all TEAEs by treatment group during the 12-week treatment period, and during the follow-up period will include:

- The number (n) and percentage (%) of patients with at least 1 TEAE by SOC and PT
- TEAEs by severity, presented by SOC and PT
- Treatment related TEAEs, presented by SOC and PT
- Serious and treatment related serious TEAEs, presented by SOC and PT
- TEAEs leading to permanent treatment discontinuation, presented by SOC and PT
- TEAEs leading to death, presented by SOC and PT

For each TEAE summary presented by SOC and PT, the summary table will be sorted by decreasing frequency of SOC and PT. For TEAE summary presented by PT, the summary table will be sorted by decreasing frequency of PT of the dupilumab arm.

Counts will be provided for each patient within each SOC and PT. Percentages will be calculated using the number of patients from the SAF in each group.

For details on handling missing data and partial dates, see Section 6.

5.8.2. Clinical Laboratory Measurements

Laboratory measurements include clinical chemistry, hematology, and urinalysis results, and will be converted to values in standard international units. Summaries of laboratory variables will include:

- Descriptive statistics of laboratory result and change from baseline by visit, if applicable.
- The number (n) and percentage (%) of subjects with treatment-emergent PCSVs. This summary will be provided based on all patients in the SAF as well as in the subgroup of SAF patients who did not meet the PCSV criterion at baseline (normal or missing).
- Shift tables based on baseline normal/abnormal will be presented

5.8.3. Vital Signs

Vital signs (temperature, pulse, blood pressure, and respiration rate) will be listed and summarized by baseline and change from Baseline to each scheduled assessment time with descriptive statistics.

The number and percentage of patients with a treatment-emergent potentially clinically significant value (PCSV) will be summarized for each vital sign variable.

5.8.4. Electrocardiography (ECG)

ECG status (i.e., normal, abnormal but not clinically significant, abnormal and clinically significant) will be reported.

5.8.5. Physical Exams

Physical examination findings at baseline as well as post-treatment abnormal findings by body system and status (normal, abnormal and not done) will be provided with Listing and Tables if applicable.

6. DATA HANDLING CONVENTIONS

6.1. Data Handling Convention for Missing Data

No missing data imputation is planned in this study unless specified otherwise.

For categorical variables, patients with missing data are not included in calculations of percentages unless otherwise specified. When relevant, the number of patients with missing data is presented.

6.1.1. Medication

To determine whether a medication is pre-treatment medication or concomitant medication or both, the missing medication start date is estimated as early as possible, and the missing medication end date is estimated as late as possible. If the medication start date is missing, the onset day will not be calculated in medication listings.

Concomitant medication start date

The imputation rule for concomitant medication start date is the same as AE start date.

Concomitant medication end date

If end day is missing, and end month and year are not missing: Impute end date using the last day of the month. If this leads to a date after end of study follow up date, use the last visit study date instead. Imputation flag is 'D'.

If end month is missing, and end year is not missing: Impute end date using 31 December as the day and month. If this leads to a date after end of study follow up date, use the last study visit date instead. Imputation flag is 'M'.

If end year is missing: Impute date using the end of last study visit date. Imputation flag is 'Y'.

6.1.2. PCSV

Patients who had post-baseline PCSV, but missing baseline value will be regarded as having treatment emergent PCSV. Refer to [Appendix](#) for PCSV table.

6.2. Unscheduled visits

Unscheduled visit measurements of laboratory data, vital signs, and ECG will be included in the computation of baseline, worst values, and PCSVs, if applicable.

7. INTERIM ANALYSIS

No interim analysis was planned for this study.

8. SOFTWARE

All analyses will be done using SAS Version 9.4 or above.

10. APPENDIX

10.1. Criteria for Potentially Clinically Significant Values (PCSV)

CRITERIA for POTENTIALLY CLINICALLY SIGNIFICANT VALUES (PCSV)

Parameter	PCSV	Comments
Clinical Chemistry		
ALT	By distribution analysis: >3 ULN >5 ULN >10 ULN >20 ULN	Enzymes activities must be expressed in ULN, not in IU/L. Concept paper on DILI – FDA draft Guidance Oct 2007. Internal DILI WG Oct 2008. Categories are cumulative. First row is mandatory. Rows following one mentioning zero can be deleted.
AST	By distribution analysis: >3 ULN >5 ULN >10 ULN >20 ULN	Enzymes activities must be expressed in ULN, not in IU/L. Concept paper on DILI – FDA draft Guidance Oct 2007. Internal DILI WG Oct 2008. Categories are cumulative. First row is mandatory. Rows following one mentioning zero can be deleted.
Alkaline Phosphatase	>1.5 ULN	Enzymes activities must be expressed in ULN, not in IU/L. Concept paper on DILI – FDA draft Guidance Oct 2007. Internal DILI WG Oct 2008.
Total Bilirubin	>1.5 ULN >2 ULN	Must be expressed in ULN, not in μ mol/L or mg/L. Categories are cumulative. Concept paper on DILI – FDA draft Guidance Oct 2007. Internal DILI WG Oct 2008.
Conjugated Bilirubin	>35% Total Bilirubin and TBILI>1.5 ULN	Conjugated bilirubin dosed on a case-by-case basis.
(ALT or AST) and Total Bilirubin	((ALT \leq 3 \times ULN and AST \leq 3 \times ULN) or TBILI \leq 2 \times ULN) at baseline and ((ALT $>$ 3 \times ULN or AST $>$ 3 \times ULN) and TBILI $>$ 2 \times ULN) post-baseline	

Regeneron Pharmaceuticals, Inc.**Protocol Number R668-AS-1903****Statistical Analysis Plan v1.0****CRITERIA for POTENTIALLY CLINICALLY SIGNIFICANT VALUES (PCSV)**

Parameter	PCSV	Comments
CPK	>3 ULN >10 ULN	FDA Feb 2005. Am J Cardiol April 2006. Categories are cumulative. First row is mandatory. Rows following one mentioning zero can be deleted.
CLcr (mL/min) (Estimated creatinine clearance based on the Cokcroft-Gault equation)	<15 (end stage renal disease) ≥15 - <30 (severe decrease in GFR) ≥30 - < 60 (moderate decrease in GFR) ≥60 - <90 (mild decrease in GFR) ≥ 90 (normal GFR)	FDA draft Guidance 2010 Pharmacokinetics in patients with impaired renal function-study design, data analysis, and impact on dosing and labeling
eGFR (mL/min/1.73m ²) (Estimate of GFR based on an MDRD equation)	<15 (end stage renal disease) ≥15 - <30 (severe decrease in GFR) ≥30 - < 60 (moderate decrease in GFR) ≥60 - <90 (mild decrease in GFR) ≥ 90 (normal GFR)	FDA draft Guidance 2010 Pharmacokinetics in patients with impaired renal function-study design, data analysis, and impact on dosing and labeling
Creatinine	≥150 µmol/L (Adults) ≥30% change from baseline ≥100% change from baseline	Benichou C., 1994.
Uric Acid		Harrison- Principles of internal Medicine 17 th Ed., 2008.
Hyperuricemia	>408 µmol/L	
Hypouricemia	<120 µmol/L	
Blood Urea Nitrogen	≥17 mmol/L	
Chloride	<80 mmol/L ≥115 mmol/L	

Regeneron Pharmaceuticals, Inc.

Protocol Number R668-AS-1903

Statistical Analysis Plan v1.0

CRITERIA for POTENTIALLY CLINICALLY SIGNIFICANT VALUES (PCSV)

Parameter	PCSV	Comments
Sodium	≤ 129 mmol/L ≥ 160 mmol/L	
Potassium	<3 mmol/L ≥ 5.5 mmol/L	FDA Feb 2005.
Total Cholesterol	≥ 7.74 mmol/L	Threshold for therapeutic intervention.
Triglycerides	≥ 4.6 mmol/L	Threshold for therapeutic intervention.
Lipasemia	≥ 3 ULN	
Amylasemia	≥ 3 ULN	
Glucose		
Hypoglycaemia	≤ 3.9 mmol/L and $<LLN$	ADA May 2005.
Hyperglycaemia	≥ 11.1 mmol/L (unfasted); ≥ 7 mmol/L (fasted)	ADA Jan 2008.
HbA1c	$>8\%$	
Albumin	≤ 25 g/L	
CRP	>2 ULN or >10 mg/L (if ULN not provided)	FDA Sept 2005.
Hematology		
WBC	<3.0 Giga/L (Non-Black); <2.0 Giga/L (Black) ≥ 16.0 Giga/L	Increase in WBC: not relevant. To be interpreted only if no differential count available.
Lymphocytes	>4.0 Giga/L	
Neutrophils	<1.5 Giga/L (Non-Black); <1.0 Giga/L (Black)	International Consensus meeting on drug-induced blood cytopenias, 1991. FDA criteria.
Monocytes	>0.7 Giga/L	
Basophils	>0.1 Giga/L	
Eosinophils	>0.5 Giga/L or $>ULN$ (if $ULN \geq 0.5$ Giga/L)	Harrison- Principles of internal Medicine 17 th Ed., 2008.

Regeneron Pharmaceuticals, Inc.**Protocol Number R668-AS-1903****Statistical Analysis Plan v1.0****CRITERIA for POTENTIALLY CLINICALLY SIGNIFICANT VALUES (PCSV)**

Parameter	PCSV	Comments
Hemoglobin	>115 g/L at baseline and \leq 115 g/L post-baseline for Male; >95 g/L at baseline and \leq 95 g/L post-baseline for Female <185 g/L at baseline and \geq 185 g/L post-baseline for Male; <165 g/L at baseline and \geq 165 g/L post-baseline for Female Decrease from baseline by \geq 20 g/L	Three criteria are independent. Criteria based upon decrease from baseline are more relevant than those based on absolute value. Other categories for decrease from baseline can be used (\geq 30 g/L, \geq 40 g/L, \geq 50 g/L).
Hematocrit	>0.37 v/v at baseline and \leq 0.37 v/v post-baseline for Male; >0.32 v/v at baseline and \leq 0.32 v/v post-baseline for Female <0.55 v/v at baseline and \geq 0.55 v/v post-baseline for Male; <0.5 v/v at baseline and \geq 0.5 v/v post-baseline for Female	
RBC	\geq 4 Tera/L at baseline and $<$ 4 Tera/L post-baseline for Male; \geq 3 Tera/L at baseline and $<$ 3 Tera/L post-baseline for Female <7 Tera/L at baseline and \geq 7 Tera/L post-baseline for Male; <6 Tera/L at baseline and \geq 6 Tera/L post-baseline for Female	Unless specifically required for particular drug development, the analysis is redundant with that of Hb. Otherwise, consider FDA criteria.
Platelets	<100 Giga/L \geq 700 Giga/L	International Consensus meeting on drug-induced blood cytopenias, 1991.
Urinalysis		
pH	\leq 4.6 \geq 8	

Regeneron Pharmaceuticals, Inc.**Protocol Number R668-AS-1903****Statistical Analysis Plan v1.0****CRITERIA for POTENTIALLY CLINICALLY SIGNIFICANT VALUES (PCSV)**

Parameter	PCSV	Comments
Vital signs		
HR	≤ 50 bpm and decrease from baseline ≥ 20 bpm ≥ 120 bpm and increase from baseline ≥ 20 bpm	To be applied for all positions (including missing) except STANDING.
Respiratory rate	≥ 12 breaths per minute at baseline and <12 breaths per minute post-baseline ≤ 20 breaths per minute at baseline and >20 breaths per minute post-baseline	To be applied for all positions (including missing) except STANDING.
SBP	≤ 95 mmHg and decrease from baseline ≥ 20 mmHg ≥ 160 mmHg and increase from baseline ≥ 20 mmHg	
DBP	≤ 45 mmHg and decrease from baseline ≥ 10 mmHg ≥ 110 mmHg and increase from baseline ≥ 10 mmHg	To be applied for all positions (including missing) except STANDING.
Orthostatic Hypotension		
Orthostatic SDB	≤ -20 mmHg	
Orthostatic DBP	≤ -10 mmHg	

[figure not shown]
Regeneron Pharmaceuticals, Inc.**Protocol Number R668-AS-1903****Statistical Analysis Plan v1.0****CRITERIA for POTENTIALLY CLINICALLY SIGNIFICANT VALUES (PCSV)**

Parameter	PCSV	Comments
Weight	$\geq 5\%$ increase from baseline $\geq 5\%$ decrease from baseline	FDA Feb 2007
ECG	Ref.: ICH E14 guidance (2005) and E14 Q&A (2012), and Cardiac Safety Research Consortium White Paper on PR and QRS (Nada et al. Am Heart J. 2013; 165(4) : 489-500)	
HR	≤ 50 bpm post-baseline and decrease from baseline by ≥ 20 bpm ≥ 120 bpm post-baseline and increase from baseline by ≥ 20 bpm	Categories are cumulative Ref.: CPMP 1997 guideline
PR	≥ 220 ms post-baseline and increase from baseline by ≥ 20 ms	Ref.: CPMP 1997 guideline.
QRS	<120 ms at baseline and ≥ 120 ms post-baseline	Ref.: CPMP 1997 guideline.

Regeneron Pharmaceuticals, Inc.**Protocol Number R668-AS-1903****Statistical Analysis Plan v1.0****CRITERIA for POTENTIALLY CLINICALLY SIGNIFICANT VALUES (PCSV)**

Parameter	PCSV	Comments
QTcB/QTcF	
Borderline: <431 ms at baseline and 431-450 ms post- baseline for Male; <451 ms at baseline and 451-470 ms post- baseline for Female
 
Prolonged: ≤450 ms at baseline and >450 to <500 ms post-baseline for Male; ≤470 ms at baseline and >470 to <500 ms post-baseline for Female
 
<500 ms at baseline and ≥500 ms post- baseline
 
Increase from baseline
 
Borderline: Increase from baseline by 30- 60 ms
 
Prolonged: Increase from baseline by >60 ms
	
Ref.: CPMP 1997 guideline.
 
5 independent criteria

Signature Page for VV-RIM-00299848 v1.0

Approval/eSignature		
		15-May-2023 16:10:16 GMT+0000

Signature Page for VV-RIM-00299848 v1.0 Approved
